The pre-supplemental motor area (preSMA) and dorsal anterior cingulate cortex (dACC) have been shown to play a role in episodic memory and word retrieval. Although the hippocampus is a brain structure most often associated with early deficits in amnesic mild cognitive impairment (aMCI), the earliest clinical threshold preceding dementia, the dACC is another node in the neural network for episodic memory that may be more accessible to neurostimulation methods. Entraining the preSMA/dACC circuits with 10 sessions of neurostimulation could be used to improve cognitive functioning evaluated by EEG-based and neuropsychological measures. High-definition transcranial direct current stimulation (HD-tDCS) is one neurostimulation approach that uses an array of small electrodes to pass a low level current through targeted brain regions (e.g., anterior cingulate cortex) to modulate neuronal activity and brain circuitry.

Purpose:

The purpose of this study is to examine the efficacy of HD-tDCS to the preSMA/dACC region and its influence on EEG and neuropsychological measures in patients with aMCI.

Primary Objective:

[figure not shown]
- Determine if HD-tDCS enhances verbal episodic memory functioning in aMCI

Secondary Objective:

- Determine if HD-tDCS enhances word retrieval functioning (i.e., language) in aMCI
- Evaluate if cognitive changes produced from HD-tDCS persist for 2 months
- Evaluate if HD-tDCS modulates EEG-derived neural synchronizations associated with memory functions to inform potential target engagement

Design:

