Participants with a clinical diagnosis of aMCI will be enrolled and randomized to receive 10 sessions of either 1mA HD-tDCS or sham stimulation. All participants will be stable on oral medications for a minimum of 1 month before initiation of study procedures. Each HD-tDCS session will be 20 minutes in duration and have electrodes configured to target the preSMA/dACC, consisting of a single anode at Fz (1 mA) and 4 cathodes (all at 0.25 mA) at FP1, FP2, F7, F8. EEG and neuropsychological tasks will be completed at baseline, immediate after session 10, and a 2-month follow-up. Participants randomized into the sham group will have the opportunity to return after 2 months for an open-label phase to receive active treatment while being unblinded to their condition group. For participants crossing over from sham-to-active treatment in the open-label phase, EEG and neuropsychological tests will be obtained again immediately following the 10 HD-tDCS sessions and at a 2-month follow-up. With this design, we expect a 15% attrition rate and plan on enrolling ~30 adults to achieve our completed sample of 24.

Below is a table summarizing the study visits. In Phase 1, participants will be randomized to active or sham stimulation and complete 12 visits. In Phase 2, participants in the sham group will be invited to receive the active condition as an open-label phase, which would involve 11 additional visits in the study.

SUMMARY OF VISITS		
Phase 1	PROCEDURES	TIME
Visit 1	Pre-testing neuropsychological assessment/semantic EEG	3 hours
Visits 2-10	HD-tDCS active or sham stimulation	30 minutes
Visit 11	HD-tDCS active or sham stimulation and post-testing neuropsychological assessment/semantic EEG	3 hours

Visit 12	8-week follow-up assessments/semantic EEG	3 hours
Phase 2	Open-label Phase	
Visits 13-21	HD-tDCS active stimulation (for Phase 1 sham group participants only)	30 minutes
Visit 22	HD-tDCS active stimulation and post-testing neuropsychological assessment/semantic EEG	3 hours
Visit 23	8-week follow-up assessments/semantic EEG	3 hours

Inclusion criteria:

1. Age 55 and older
2. Fluent in English
3. Active diagnosis of aMCI
4. Deficit in at least one measure of language functioning, defined as performing >1 standard deviation below the standardized score mean on either the Boston Naming Test, phonemic fluency, or semantic fluency measures

Exclusion criteria:

1. Substance use disorder within past year
2. Has metal fragments or implants in skull/head

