3. Profound vision or hearing impairment that interferes with testing
4. Major neurologic conditions (stroke, epilepsy, brain tumor, concussion in past year)
5. Current medication use known to alter HD-tDCS reactivity: amphetamines, L-dopa, carbamazepine, sulpiride, pergolide, lorazepam, dextromethorphan, D-cycloserine, flunarizine, or ropinirole

If a medical condition becomes apparent during the evaluation or follow-up that indicates an increased risk, then the subject's involvement in the study will be discontinued.

Procedures:

HD-tDCS arms of intervention: The study has 2 arms of intervention. The HD-tDCS treatment uses a cap with arrays of electrodes, combinations of which can be optimized for targeting delivery of electrical current to specific brain regions. HD-tDCS is delivered with sintered 12 mm diameter Ag/AgCl disc electrodes. The EEG cap is gently secured on the head of a subject and positioned with Cz at the vertex, as measured using surface anatomical landmarks, and defined as the intersection of the nasion-inion and interaural lines. Electrical stimulation will be performed while awake and at rest using a constant current controlled device manufactured by Neuroelectrics (Starstim system). Electrodes will be filled with a conductive gel. Contact quality and impedance levels (< 10 kOhms) will be verified for each electrode before each stimulation session begins. Daily HD-tDCS sessions lasting for 20 minutes (total of about 30-40 minutes including preparation) will be administered over 2 weeks (5 daily sessions each week). After each session, patients will be administered a standard post-treatment symptom questionnaire (e.g., assessing for skin irritation, fatigue).

Arm 1: For the 1 mA active HD-tDCS condition, administration parameters will consist of the stimulation being ramped up over 60 seconds until it reaches 1 mA and then maintained for 20 minutes. The anode will be placed over Fz according to the International 10-20 EEG system, corresponding to the approximate location of the dACC. Four return cathodal electrodes will be placed at FP1, FP2, F7, F8.

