Recruitment strategy: Participants will be recruited from memory specialty clinics in Dallas, Texas, referred by clinicians in neurology, psychiatry, and neuropsychology. Recruitment will occur at clinics situated at UT Southwestern comprised of a Neuropsychology Clinic and a separate Neurology Memory Clinic, wherein each receives internal and external referrals to clinically diagnose patients with aMCI. Our catchment area will extend outside UTSW to the broader Dallas-Fort Worth Metroplex and involve Baylor Medical Center's AT&T Memory Center. Clinician referrals and self-referrals will primarily be used to identify subjects directly for screening/recruitment. Strategies for obtaining these will include 1) providing study-related information with colleagues at selected Clinics via e-newsletters and university presentations, 2) placing flyers in exam rooms and waiting areas at clinic facilities, 3) advertising on the UT Southwestern website, and 4) outreach to regional community sources. Digital tools in the electronic health record for UT Southwestern will also be leveraged to create a data registry for screening of eligible patients who opted to be contacted for research.

Screening and consenting strategy: Prospective participants will undergo an initial phone screening to ensure basic eligibility criteria are met (e.g., diagnosis of aMCI, conditions in their medical history, medications). Prospective participants meeting pre-screening inclusion/exclusion criteria will be scheduled an appointment to review the study procedures and Consent Form. Study staff will go over the consent form in detail with the prospective participant and answer any questions about the procedures.

Participants or the legal authorized representative will be asked to sign the Consent Form if they understand the study procedures, appreciate potential risks/benefits, and desire to be in the study.

Timing and procedures of follow-up: Cognitive and EEG evaluations will be completed immediately after session 10 and 2-months later. Patients will be called back for the 2-month follow-up. For individuals who received the sham condition, they will be invited back for an open-label phase of active HD-tDCS. Cognitive and EEG outcomes will be obtained immediately after session 10 and 2-months later during the open-label phase of sham crossing over to active treatment.

Cognitive Outcomes:

Primary

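### Read literally, the discontinuation rule ends assessment along with stimulation; applied after Visit 11, it can lose the 2-month data without preventing any Phase 1 stimulation

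*Combined protocol and SAP*

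**What the plan says.** The rule closes the Exclusion criteria. Its trigger is that a "medical condition becomes apparent during the evaluation or follow-up that indicates an increased risk"; its consequence is that the subject's "involvement in the study will be discontinued". It does not say what the risk would come from, and it has no intermediate step in which stimulation stops but assessment continues. The section on subject safety monitoring covers oversight, recording and IRB reporting, and adds no such step. Consent pages are not in the supplied text and could not be checked.

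The surrounding plan is as follows.

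- **Stimulation.** Under Procedures, the sessions "will be administered over 2 weeks (5 daily sessions each week". The visit table in the Design section puts nine sessions at Visits 2 to 10 and the tenth at Visit 11, together with post-testing.
- **Visit 12.** The table lists "8-week follow-up assessments/semantic EEG" and no stimulation.
- **Objective.** One secondary objective is "Evaluate if cognitive changes produced from HD-tDCS persist for 2 months".
- **Phase 2.** Sham participants have the "opportunity to return after 2 months for an open-label phase".
- **Analysis.** Under Statistical analysis, the ANCOVA compares performance after all sessions, adjusted for the pre-treatment score. A mixed model covers the three assessment times, and participants who lack a time point stay in the analysis.

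**The concern.** Stopping treatment and leaving the study are different events, and the rule merges them. After Visit 11 an active-arm participant has no stimulation left to stop. A sham participant faces only Phase 2, and barring Phase 2 gives that protection without touching Visit 12. At that stage, removal from the study therefore adds no protection against stimulation, but it can cost the 2-month assessment.

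The scores lost this way would be missing for a health reason, and health may also affect cognition. If lower scorers are removed mainly from the active arm, persistence looks better than it is; if mainly from the sham arm, it looks worse. The mixed model keeps the earlier scores of a removed participant, which may already partly reflect the condition. It cannot recover a change that arose after Visit 11 and was never measured.

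A related gap concerns anyone who stops stimulation early. The ANCOVA score is defined as following all sessions, so the plan does not say how such a participant would be analysed.

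**Working it through.** **1. What remains after Visit 11.** Visits 2 to 10 give 9 sessions and Visit 11 gives 1, so 9 + 1 = 10, the planned number. Phase 1 sessions left after Visit 11: 0. Phase 1 assessments are at Visits 1, 11 and 12, so a removal between Visits 11 and 12 loses 1 of 3, and that one is the only 2-month measurement in Phase 1.

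**2. Which analyses are touched.** The ANCOVA outcome is collected at Visit 11, so a later removal leaves it intact. A removal before Visit 11 would lose it. The rule speaks of evaluation and follow-up and leaves open whether treatment visits count.

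**3. Numbers per arm.** The Design section expects 15% attrition and about 30 enrolled "to achieve our completed sample of 24". Check: 24 / 0.85 = 28.2, rounded up to 29, which agrees with about 30. Randomisation is 1:1, so 30 / 2 = 15 enrolled per arm. Removals under this rule are part of attrition and come out of the 15.

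**4. Illustration of size.** The documents give neither the frequency of removals nor the scores that would be lost, so both are assumed:

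- k = 1 or 2 participants removed, all from one arm;
- they would have scored d = 5 or 10 T-points below those retained;
- no other loss, and observed means are compared.

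If the retained mean is m, the full-arm mean is ((15 − k)m + k(m − d)) / 15 = m − kd/15. The observed arm mean is therefore off by kd/15. The last column divides by 5, the T-score gain that Statistical analysis uses for clinically meaningful change.

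| k | d | shift = kd/15 | shift / 5 |
|---|---|---|---|
| 1 | 5 | 0.33 | 7% |
| 1 | 10 | 0.67 | 13% |
| 2 | 5 | 0.67 | 13% |
| 2 | 10 | 1.33 | 27% |

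If instead 12 are retained in the arm and the k removed are added back, the shift is kd/(12 + k): from 5/13 = 0.38 to 20/14 = 1.43. The order of size is the same.

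The shift is 0 if both arms lose the same number with the same d. It is smaller in the mixed model to the extent that earlier scores predict Visit 12.

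**The case against.** The strongest reply is that the rule does not say what the risk is from, so its effect after Visit 11 is not settled. If it means risk from stimulation, an active-arm participant has none left and the rule arguably does not apply. If it means risk from the assessment visit, cancelling Visit 12 is right. This stands: the loss follows from a literal or cautious application of the wording, not with certainty.

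The occasions for a trigger are also few. About 8 of the roughly 10 Phase 1 weeks (2 + 8) fall after the last session, but that is calendar time, not chance of detection. The remaining scheduled contacts are the call-back ("Patients will be called back for the 2-month follow-up") and Visit 12 itself, and a condition found at Visit 12 may still leave some or all of the data collected. This also stands, and it keeps the likely number of losses low.

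Third, the plan already allows for attrition and keeps participants with missing time points. This helps only in part, because retaining a participant in the model does not supply a score that was never taken.

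A reader might infer that the rule always cancels the 2-month visit, or that it biases the primary result. The documents support neither: the risk is undefined, and the primary score is already in hand at Visit 11. A reader might also take removals out of 12 per arm, which would give a larger shift. But 24 is the number left after attrition, so that denominator has already excluded those removed.

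**Conclusion.** The point holds as a minor one. In the supplied text, the sole discontinuation rule is mandatory and ends study involvement without separating treatment from assessment. Applied as written after Visit 11, it prevents no Phase 1 stimulation and can lose health-related data for a named secondary objective. The primary ANCOVA is at risk only if the rule is also used before Visit 11.

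The true size is unknown and could be zero. The range of about 0.3 to 1.3 T-points rests wholly on the assumed k and d, on one-sided loss, and on comparing observed means, which is not the planned mixed-model analysis. It shows that one or two removals could matter in arms of this size, not that they will occur.

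**What to change.** Replace the closing sentence of the Exclusion criteria with wording such as:

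> If a condition that indicates an increased risk from stimulation is found at any time, including at a stimulation visit, no further stimulation is given and the participant does not enter Phase 2. The participant remains in the study for the outstanding cognitive and EEG assessments of the current phase, on their planned dates, and for adverse-event follow-up, unless consent is withdrawn or the assessment itself is judged unsafe. Both arms receive the same wording. The date and reason are recorded.

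Using the same wording in both arms avoids disclosing allocation before Visit 12. The clinical criterion for increased risk stays with the sponsor.

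Add to Statistical analysis that scores collected after early stopping are analysed in the randomised group, in both the ANCOVA and the mixed model. For an early stopper, the ANCOVA score would be the assessment on the date when Visit 11 would have fallen.

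The cost is a short amendment with IRB review, possibly new consent wording, and a few already scheduled visits kept. An early stopper's Visit 11 becomes an assessment without stimulation. If Phase 1 visits are already complete, what remains is to report each discontinuation by arm, date and reason.

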Arm 2: For the sham condition, parameters will consist of the current being ramped up over 60 seconds until it reaches 1 mA and then stopped. This allows for the same scalp sensation for both the sham and active condition so that subject and experimenter will remain blinded. This ramp up for one minute and then stopped and off for 20 minutes will be given each 20-minute sham session to keep the timing and subjective experience similar to the active condition.

All HD-tDCS protocols for participants will be pre-programmed into the Neuroelectrics software. HD-tDCS protocols will be set by a PI ([name]) for each participant using an encrypted approach, labeling with the participant research identifier to conceal condition assignment. Aside from the PI, other study team members will be unaware of the HD-tDCS condition allocation to preserve blinding.

Randomization: Participants will be randomized at a ratio of 1:1 to receive active 1 mA and sham conditions. Randomization of HD-tDCS condition assignments will be generated by a digital program, and the assignments (Protocol 1 = active or 2= sham) recorded in an encrypted spreadsheet that only the PI ([name]) has access to.

Blinding: Participants will be informed that sham and active HD-tDCS will be used in the study, but they will be blinded to condition. Aside from the PI ([name]), other study team members who deliver HD-tDCS and perform assessments will be blinded to HD-tDCS condition. Both the subject and study personnel will complete a questionnaire to check if blinding was successful.

Sample size calculation: Pre-study power analyses were conducted for the most power intensive phase (Phase 1 - randomized controlled trial) using a clinically relevant effect size derived from our prior studies. A sample size of 20 provides 80% power to detect a $f = .27$ effect size for the analysis of the primary outcome using an analysis of covariance model, assuming the baseline covariate of performance explains $R^2 = .2$ and $\alpha = .05$. Given that both our and other's research without intervention suggests that effect sizes tend to be larger in EEG compared to cognitive measures, we expect the effect size of EEG outcomes to be at least equivalent to cognitive outcomes.

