Time-frequency decomposition will be performed using the newtimef function in EEGLAB. For each channel, single-trial EEG data will be transformed into event-related spectral perturbation (ERSP) values. The analysis will use the Fast Fourier transform with the following parameters: a Hanning-tapered sliding window length of 250 ms, a zero-padding ratio of 4, and 100 linearly spaced time points across the entire epoch. Frequencies between 1 and 30 Hz will be analyzed with a linear scaling at 1 Hz intervals. A linear detrend will be applied to each epoch. Spectral power will be log-transformed and expressed in decibel (dB) units. Baseline correction within each 1 Hz frequency interval will be performed for each single trial by subtracting the average power between -700 and -100 ms pre-stimulus onset from each time point post-stimulus onset to calculate ERSP using a gain model. Data from the theta (4-7 Hz) and alpha (8-12 Hz) frequency bands will be averaged at each electrode-time point for statistical analysis.

Changes to outcomes: There were no changes to outcomes after the trial commenced.

Subject safety monitoring: All HD-tDCS and EEG sessions will be overseen by the PI. All safety precautions recommended by scientific literature and the UT Southwestern IRB will be carefully followed. All adverse events volunteered by the subject or elicited by the research team will be recorded in the subjects' research file. All adverse events will be reported within one week to the IRB. Any severe adverse events will be reported within 24-48 hours to the IRB.

In order to safeguard our participants from a breach in confidentiality, the data is coded with a unique semi-random subject identifier (URSI). All data after initial entry into the study is coded based on the participant's number. A digital file containing completed questionnaires and assessments from the experimental session will be maintained with the URSI number. These files will be kept in an encrypted, IRB approved database (RedCap).

Statistical analysis

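### The structured symptom questionnaire is scheduled only after stimulation sessions; none is stated before session 1 or at the 2-month visits (Visits 12 and 23)

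*Combined protocol and SAP*

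**What the plan says.** Under Procedures (HD-tDCS arms of intervention) the protocol names one symptom instrument and fixes its timing: "After each session, patients will be administered a standard post-treatment symptom questionnaire (e.g., assessing for skin irritation, fatigue". Sessions "will be administered over 2 weeks (5 daily sessions each week". The instrument is not reproduced.

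Under Timing and procedures of follow-up, the later evaluations are described by content: "Cognitive and EEG evaluations will be completed immediately after session 10 and 2-months later". No symptom form is mentioned there. The visit table under Design labels Visits 12 and 23 "8-week follow-up assessments/semantic EEG". That table is a summary and lists no symptom form at any visit, even those where one is planned, so nothing here rests on its silence.

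Safety is also covered in general terms. Under Subject safety monitoring, "All HD-tDCS and EEG sessions will be overseen by the PI" and "All adverse events volunteered by the subject or elicited by the research team will be recorded in the subjects' research file". The sentence after the exclusion criteria ends a participant's involvement if a medical condition that raises risk comes to light during evaluation or follow-up. The only other questionnaire with a stated purpose is the check on blinding.

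**The concern.** Two pieces of information are not scheduled.

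- **A rating before any exposure.** Fatigue, one of the protocol's two example symptoms, is non-specific. If a participant reports it after session 1, the planned forms hold no earlier rating to compare it with.
- **A structured check after treatment ends.** The last stated form follows session 10. The study asks whether cognitive effects last 2 months, but it names no instrument for asking whether unwanted effects do. At the 2-month visit this depends on what a participant with amnestic MCI volunteers, or on questions whose timing and content are not set out.

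At stake is the attribution of symptoms in individual participants, and the record of effects still present at 2 months. The efficacy results are not at stake.

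**Working it through.** The plan gives no figure on this point to reproduce. The check is a count of stated symptom forms against the visit table, followed by a comparison of the relevant sections.

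**Forms stated** (inputs: visit table under Design; one form per session from Procedures)

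- Phase 1: Visits 2-10 (9 sessions) + Visit 11 (1 session) = 10 forms.
- Phase 2, sham crossovers only: Visits 13-21 (9) + Visit 22 (1) = 10 forms, assuming the per-session rule also covers the open-label phase.
- Full crossover: 10 + 10 = 20 forms.
- Before session 1: 0. At Visit 12: 0. At Visit 23: 0.

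**What else could supply the missing ratings**

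- *PI oversight.* Visits 1, 12 and 23 all include EEG, so they fall under the oversight commitment. Events can be elicited and recorded there, but no instrument or time for eliciting them is given.
- *Discontinuation rule.* It applies during evaluation and follow-up. It acts on conditions that raise risk and does not grade mild symptoms.
- *Sham arm.* In Phase 1, randomisation balances pre-existing symptoms on average, so post-session symptoms can be compared between arms without a baseline rating. It does not tell us whether one person's symptom was already there.
- *Sham-session forms for crossovers.* Someone entering Phase 2 has up to 10 earlier forms. These follow cap, gel and a brief current, since for sham "parameters will consist of the current being ramped up over 60 seconds until it reaches 1 mA and then stopped". They are a useful comparison but not ratings before exposure. Phase 1 active participants have no form that precedes active current.
- *Phase 2 control.* Sham participants may "return after 2 months for an open-label phase to receive active treatment while being unblinded to their condition group". That phase is unblinded with no concurrent comparator, so each person's own earlier ratings matter more.

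**Forms to add**

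- Phase 1: 1 before session 1 + 1 at Visit 12 = 2, so 10 + 2 = 12.
- Phase 2: 1 at Visit 23, so 10 + 1 = 11. If there is a long gap before Visit 13, add 1 more: 12.
- Full crossover: 20 + 3 = 23, or 20 + 4 = 24 with the long gap.

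**Time** (assumed 2 to 5 minutes per form; the documents give none)

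- Phase 1, per person: 2 × 2 = 4 to 2 × 5 = 10 minutes.
- Phase 2, per person: 2 to 5 minutes, or 4 to 10 with the extra form.
- Share of a 3-hour visit: 2/180 = 1.1% to 5/180 = 2.8%.
- Share of a 30-minute visit, if the first form is given at Visit 2: 2/30 = 6.7% to 5/30 = 16.7%.
- Whole trial, with about 30 enrolled, 1:1 allocation and all 15 sham participants assumed to cross over: 30 × 2 + 15 × 1 = 75 forms, or 150 to 375 minutes (2.5 to 6.25 hours). With the extra form for all 15: 90 forms, or 180 to 450 minutes (3 to 7.5 hours).

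**The case against.** The strongest reply is that this is a preference, not a defect. Safety and tolerability are not listed objectives, and the Statistical analysis section plans no symptom analysis. The visits without a form already have PI oversight and open-ended event recording, with no stated end date. Sham handles background symptoms on average. The form, which nobody outside the study can see here, may already ask about change or relation to stimulation. Most of this stands, and it is why the point is rated low.

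It does not remove the point entirely. A form that asks about change would narrow the baseline gap but would still not be given at 2 months. Oversight makes elicitation possible without making it uniform across participants.

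Three stronger readings are tempting, and the documents support none of them:

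- A reader might infer that safety goes unmonitored before treatment and at follow-up. The safety section and the discontinuation sentence say otherwise; only a structured instrument is absent.
- A reader might infer that a symptom reported after session 1 can never be classed as new or pre-existing. That depends on the content of a form that is not reproduced.
- A reader might infer from the 8 weeks without a form that events are being missed at some rate. The documents give no event rate or onset time, and no stimulation is given in that interval, so its length does not measure risk.

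**Conclusion.** The gap is real but small. As written, the plan yields 10 post-session forms per course and no structured symptom rating before session 1, at Visit 12 or at Visit 23. The consequence is limited to individuals: a non-specific symptom may not be separable from a pre-existing one, and symptoms still present at 2 months have no structured record. The Phase 1 comparison between arms, the efficacy analyses and every stated figure are unaffected. No number of missed events can be given.

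The baseline part assumes that the questionnaire does not itself ask about change or relation to stimulation. The 2-month part does not need that assumption. Severity is COULD: a cheap improvement to the plan, not the correction of an error.

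**What to change.** Use the existing questionnaire, with any treatment-specific items adapted, at these points:

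1. Once before session 1, either at Visit 1 or before stimulation at Visit 2.
2. Once at Visit 12 and, for crossovers, once at Visit 23.
3. Let Visit 12 serve as the rating before Phase 2. Repeat the form before the first open-label session only if there is a long gap before Visit 13; the length of that gap is not stated.

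Report symptoms that are new or worse than the pre-treatment rating, by arm in Phase 1 and separately for Phase 2.

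The cost is two short forms per person in Phase 1 and one in Phase 2 (two with a long gap), all at existing visits, plus a few more records to enter and summarise. Placing the first form at Visit 1 avoids taking time from a 30-minute session. One limit should be stated in the report: 8-week recall in aMCI is weak, so the 2-month form will mainly capture symptoms still present, not transient ones that have resolved.

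The protocol's statement on changes to outcomes implies that the trial has started. The forms can then help only participants still to be treated or followed up. For the others, the safety report can say that no structured baseline or 2-month rating was scheduled.
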